A clue for diagnosis of KS earlier in infancy or childhood is the presence of small penis and testes, as exemplified by a set of twins discordant for KS (5). The testes and penis of the KS affected twin only, as well as in KS boys evaluated in childhood, were small at birth and throughout adolescence (5). Gonadotropins have generally been normal (low) in childhood and tend to rise by age 12-14 years in KS boys, similar to normal boys. However, normal gonadotropins in childhood do not necessarily indicate normal testicular function. Gonadotropins in girls with Turner syndrome who have early and severe ovarian failure are also normal in childhood and rise at age 10-12 years (6).

Other signs of testicular failure in adolescence include gynecomastia, eunuchoidal body proportion with relatively longer legs and increased arm span, decreased facial, pubic, and body hair, decreased muscle mass, and feminine distribution of body fat. Testosterone levels measured prenatally and in infancy in a small number of KS males were decreased or normal (7) and remained low-normal in childhood and adulthood (5). Testicular biopsy specimens of KS infants demonstrate decreased germ cells. After puberty, hyalinization and fibrosis of the seminiferous tubules occurs with small testes and

azoospermia. Thus, the extra X chromosome affects both testicular germ cells and interstitial cells.

II. Physical phenotype

KS boys tend to be tall (average adult height of 186 cm) (8), starting in infancy and childhood, with disproportionately long legs and arms and relatively small head circumference SDS compared to height SDS (4, 5, 9, 10). Their tall stature, mainly due to increased leg length, occurs in childhood and is likely related to 47,XXY males having a third copy of the X chromosome height determining gene, SHOX, as well as delayed epiphyseal fusion on the basis of decreased sex hormone levels. The SHOX (short stature homeobox) gene was first identified as a major human growth determinant from molecular analysis of sex chromosome abnormalities associated with short stature (11). Other sex chromosome trisomies, 47,XYY males and 47,XXX females, also tend to be tall and have three copies of the SHOX gene (12). Skeletal anomalies associated with KS include osteoporosis, kyphosis, scoliosis, and pectus excavatum. KS males also have an increased risk for central obesity, starting in childhood (8).

III. Neurocognitive and behavioral phenotype

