The KS boys will be seen at 3-6-month intervals for the two-year duration of the study. On each visit, boys will receive a careful history and physical examination to include assessment of Tanner staging (73) for pubic hair development (Tanner 1 = prepubertal-Tanner 5 = fully mature) and measurement of penile length and testicular volume. At baseline, three, and every six months thereafter, we will measure height, weight, bone age (X-ray); fasting blood work to include complete blood count, serum glucose, liver function tests (SGPT), lipid panel, thyroid studies, testosterone, and free testosterone (the active form of testosterone) levels. LH, FSH and estradiol will be measured yearly. At baseline and after one year, each boy will undergo a battery of cognitive tests that will take approximately 5 to 7 hours (see below).

The form of androgen will be the oral, nonaromatizable androgen oxandrolone. This androgen is FDA-approved for the indication of wasting and has been used safely for the past 30 years to stimulate growth in girls with Turner syndrome without virilization or major side effects. The dose, 0.06 mg/kg/day, was chosen because of the extensive previous experience with the dose of 0.06 mg/kg/day used in girls with Turner syndrome. Children will be monitored closely for signs of virilization including acne, voice changes,

development of pubic hair, and excessive bone age advancement. Since oxandrolone is nonaromatizable and cannot be converted to estradiol, we do not expect any feminizing side effects such as breast development to occur.

Safety results necessitating an approximate 10-50% reduction in medication dose or stopping the medication:

1. Bone age advancement exceeding 12 months per 6-month interval, with bone age exceeding chronologic age.
2. Signs of early pubertal development for age, including pubic hair development in boys less than 8 years of age.
3. Systolic blood pressure exceeding 95th %ile for age.
4. Diastolic blood pressure exceeding 95th %ile for age.
5. LDL cholesterol greater than 159 mg/dl.
6. HDL-C less than 20 mg/dl.
7. SGPT exceeding twice the upper limit of normal.
8. Dose can be lowered at the discretion of the investigator for other reasons such as rapid growth.

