The oxandrolone dosage cannot be reduced by precisely 50% because of the nature of the oxandrolone tablets that come in a single strength, 2.5 mg. The 2.5 mg pill is scored and could be accurately split to the 1.25 mg dose. The 1.25 mg dose cannot be accurately split further. Thus, according the criteria listed above, we could reduce the 3.75 mg dose to 2.5 mg and the 2.5 mg dose to 1.25 mg. Dose reduction will therefore range from approximately 10-50%, depending on the weight of the child. If the dose needs to be reduced to less than 1.25 mg/day, we will change from daily to every other day dosing.

If at any visit the child's weight is greater than the 95th percentile, the 95th percentile weight in kg will be used to calculate the dose. If this dose reduction is implemented, then additional reductions would not be implemented at that visit for the other dose reduction criteria. At a single visit, if the dose of oxandrolone is reduced for one criterion, then the dosage is not reduced again for another study criterion.

Safety results necessitating stopping the study:

If at any point in the study, two or more patients develop severe liver function changes or hypertension, the study will be stopped. These changes have not occurred with oxandrolone used in a trial with 73 girls with Turner syndrome followed for up to four years and are therefore not expected.

Criteria for Subject Withdrawal from the study and adverse event reporting:

Subjects can withdraw from the study at any time for any reason. The PI may terminate a subject's participation due to severe adverse events, noncompliance with the study, or concerns about safety. Safety data will be reviewed on an ongoing (blinded) basis by the PI.

Study compliance: We will assess patient compliance by having the families fill out study cards when they administer all medications and return the cards as well as all used and

unused study materials at the time of their visit. All pills dispensed and returned will be counted and recorded. We are currently using this procedure in other ongoing studies and have found that it is effective.

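### Dosing on the 95th-percentile weight counts as a dose reduction and bars the safety cuts at that visit, even when the boy's tablets do not go down

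*Combined protocol and SAP*

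**What the plan says.** The rules are in the protocol's Procedures, section IV (Clinical trial substudy).

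- **The list.** It is headed "Safety results necessitating an approximate 10-50% reduction in medication dose or stopping the medication". Item 1 is "Bone age advancement exceeding 12 months per 6-month interval, with bone age exceeding chronologic age". Items 2 to 7 cover early pubertal signs, systolic and diastolic blood pressure, LDL, HDL and SGPT. Item 8 is discretionary: "Dose can be lowered at the discretion of the investigator for other reasons such as rapid growth".
- **The tablet steps.** Tablets are 2.5 mg and can be halved once, so "we could reduce the 3.75 mg dose to 2.5 mg and the 2.5 mg dose to 1.25 mg". Below 1.25 mg/day, dosing moves to alternate days.
- **The weight cap.** "If at any visit the child's weight is greater than the 95th percentile", then "the 95th percentile weight in kg will be used to calculate the dose".
- **The bar.** "If this dose reduction is implemented, then additional reductions would not be implemented at that visit for the other dose reduction criteria". The next sentence allows only one criterion-driven reduction per visit.

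Item 1 is not exempt from the bar. Nothing carries a barred reduction forward to the next visit or asks for an early recheck.

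**The concern.** The list says that certain results make a reduction or a stop necessary. The bar removes the reduction half of that response at a visit where the weight cap is used. In exchange the boy gets an adjustment that responds to his weight rather than to the safety result, and that may change nothing he swallows.

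The listed criteria are not equally exposed. Blood pressure, LDL, HDL and SGPT are levels: if still abnormal, they trigger again when next measured. Item 1 is a change over a single interval. If its cut is barred, the next visit examines a different interval.

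Boys above the weight limit are foreseeable. The Background (II, Physical phenotype) describes boys with Klinefelter's syndrome as tall from infancy and childhood, and at raised risk of central obesity from childhood. Section IV also names excessive bone-age advancement as something to be watched closely. At stake is a paediatric safety response, not the primary efficacy comparison.

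**Working it through.** **Inputs from section IV.** Dose 0.06 mg/kg/day; tablet steps 3.75 to 2.5 mg and 2.5 to 1.25 mg. No rounding rule, weight distribution or bone-age reading error is given, so anything resting on these is an assumption.

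**1. The plan's own figure.** Cut = 1 − new/old.
- 3.75 to 2.5 mg: 1 − 2.5/3.75 = 33.3%.
- 2.5 to 1.25 mg: 1 − 1.25/2.5 = 50%.

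Both lie within the stated 10–50%. The lower end depends on how doses are rounded to tablets, so it can be neither confirmed nor called wrong. The point does not depend on it.

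**2. Size of the cap against the uncapped calculated dose.** Effect = 0.06 × kg above the 95th-percentile weight. One tablet step in body weight = 1.25/0.06 = 20.8 kg. Assuming rounding to the nearest step and a uniform position within a step, the share of boys whose tablets are the same with and without the cap is 1 − excess/20.83.

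| Excess (kg) | Calculated dose removed (mg/day) | Same tablets with and without cap |
|---|---|---|
| 1 | 0.06 | 95% |
| 5 | 0.30 | 76% |
| 10 | 0.60 | 52% |

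A cut under item 1 removes 1.25 mg/day.

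**3. Effect of the cap on the dose in use.** Let W0 be the weight at the previous visit, and P0 and P1 the 95th-percentile weights at the previous and current ages. Assume that P rises with age, that the dose is recalculated from weight at each visit, and that rounding is consistent.
- Newly above the limit: W0 ≤ P0 ≤ P1, so the capped dose 0.06 × P1 is at least the previous dose 0.06 × W0.
- Already above it: the previous dose was 0.06 × P0, again no more than 0.06 × P1.

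In both cases the cap limits an increase and does not lower what the boy is taking. The exception is a boy previously dosed on his full weight because the cap came into use part-way through the trial.

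**4. Whether item 1 comes round again.** Take assumed bone-age gains of 6, 13, 6 and 6 months over four 6-month intervals, with bone age equal to chronologic age at baseline. Item 1 is met only at month 12 (gain 13, bone age 19 months on against 12 months elapsed). If the cap is used at that visit, the cut is barred. At month 18 the gain is 6, so no cut is called for.

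With reading error the answer varies widely. A simulation assumed a true gain of 18 months in the first interval and 8 in each later one, the same baseline, and independent normal reading errors with SD 1 to 8 months. Given that item 1 was met at month 6, it was met again at month 12 or 18 in 0.5% (SD 1) to 59% (SD 8) of boys. This shows only that recurrence cannot be relied on.

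**The case against.** **The bar is conditional.** It applies only if the reduction is implemented. One can fairly say that a cap leaving the tablets unchanged implements nothing, so item 1 applies in full, and that a cap removing a step has already given the same 1.25 mg cut. The first half stands as a possible reading; the text does not settle it. The second half fails, because the step is removed from an uncapped calculation and not from the dose in use (step 3 of the working).

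**Stopping remains.** The list requires a reduction or a stop, and only reductions are barred, so one could argue that stopping becomes compulsory. That reading is strained: nothing says a boy must come off the drug because his weight ruled out a smaller step. It is nevertheless true that stopping stays available at that visit, as does termination by the investigator for safety concerns, and item 8 at later visits. Ongoing safety review by the investigator and the existence of a DSMB also make an ignored event less likely. All of these are discretionary.

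**A stronger reading to avoid.** A reader might infer that a boy who stays above the 95th percentile never receives a mandated reduction during the trial. That needs the bar to recur at every capped visit. It is equally open to say that a boy already dosed on the percentile weight is not newly reduced later, which confines the loss to the first capped visit. A reader might also infer that nearly all such boys would lose an item 1 cut. That requires sustained true gains at or above the trigger itself, starting from bone age no lower than chronologic age, and the documents support neither assumption.

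**Conclusion.** The point holds as a gap in the dosing rules. As worded, using the 95th-percentile weight can displace a reduction that the same section treats as necessary, while the boy's tablets stay where they are. Item 1 is the most exposed criterion because it is tied to one interval.

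The gap follows from the wording and rests on no assumed figure. The contrast between 0.06–0.60 mg/day and 1.25 mg/day uses the protocol's dose and tablet steps with illustrative excess weights. The 95%, 76% and 52% figures rest on assumed rounding. The claim that the cap does not lower the dose in use rests on the assumptions in step 3.

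The number of boys affected cannot be estimated. It would need the share above the weight limit, the rate of item 1 events at capped visits, and how often staff would act anyway; none is given. This is a clarification worth making, of modest weight, and it does not bear on the primary inference.

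**What to change.** Replace the second weight-cap sentence with: *Using the 95th-percentile weight is not a dose reduction for this rule. If any of items 1–8 calls for a reduction at that visit, the new dose is one tablet step below the dose being taken, or the capped dose if that is lower.* Keep the limit of one reduction per visit across items 1–8.

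Tying the cut to the dose being taken prevents two steps from being stacked at one visit. Going from 3.75 to 1.25 mg would be 1 − 1.25/3.75 = 67%, outside the stated 10–50%.

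The cost is one sentence, with no new films, tests or thresholds. A few boys above the 95th percentile will take one step less, sometimes because of bone-age reading error. Boys below the limit already carry that risk.

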Patient Recruitment: The PI has the unique resource of a clinic at Thomas Jefferson University, where 60 KS boys are followed. All are untreated with any androgen. We will also recruit additional patients by notifying patient groups and physicians about the study.

PROCEDURES OF THE STUDY

I. Inclusion Criteria:

1. Karyotype diagnosis of Klinefelter's syndrome or Klinefelter's variants, including 48,XXYY and 48,XXXY
2. Chronological ages 4 to 12 years
3. No previous treatment with androgen or estrogen in past one year

II. Exclusion Criteria:

1. Major liver, kidney or other systemic disease
2. Dual diagnoses including pervasive developmental delay or autism.
3. Variant karyotypes including 46,XX males and 47,XYY males
4. A high level of mosaicism (more than 50% 46,XY cells)

III. Study Outcome:

Physical features

We will document visible phenotypic features using a digital photography system. Specific physical features examined and tests used are as follows:

1. Anthropometric measurements

1. Measurements. The clinical assessment will include measurement of height, lower segment, and arm span. Subjects' heights will be measured with a stadiometer. Measured or reported parental heights will also be recorded. Mid-parental height adjusted for the child's sex (target height) will be calculated using the formula $0.5 \times [\text{father's height (cm)} + \text{mother's height (cm)} + 13]$ (64). Target height z-scores are calculated for subjects from sex-adjusted mid-parental height obtained from the National Center for Health Statistics growth curve data (65). Arm span will be measured as the distance from right to left 3rd finger tips with patients facing the wall, with outstretched arms held parallel to the ground. Lower segment will be measured from the top of the symphysis pubis to the floor. Upper arm and lower leg circumferences will be measured. Results were converted to z-scores where possible using age- and gender-specific norms (65-67).

2. Genitalia. We will measure penile length. Standards are available for penile growth in childhood and percentiles will be recorded (68). In addition, testicular size will be assessed with the Prader orchidometer and the measured volume will be recorded.

3. Optional MRI SCAN: Patients with KS will be asked if they would have an MRI scan done at baseline and at or between the 18 and 24 month visits, when they are participating in the clinical trial.

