1. Skeletal x-rays of the hands will be obtained for all subjects. Bone age will be determined according to the method of Greulich and Pyle (69).

Cognitive Outcome summary scores (To be age-appropriate):

1. General Cognition summary score (KS males, ages 2-60)
 - a. The Differential Ability Scales-(DAS)
2. Language summary score (age-appropriate):
 - Phonological
 - a. Comprehensive test of Phonological Processing (CTOPP).
 - Verbal Memory
 - a. California Verbal Learning Test-Children's Version (CVLT)
 - b. Children's Memory Scale (CMS)-story memory.
 - Expressive
 - a. Expressive one word vocabulary test
 - b. Rapid naming (NEPSY)
 - c. Test of language Competence (TLC) – Oral Expression
 - Receptive
 - a. Peabody Picture Vocabulary Test (PPVT)
 - b. Token Test
3. Working memory/Executive function/Attention summary score
 - a. Digit span backwards (DAS)

- b. Connors' Continuous Performance Test II (CPT II) and Kiddie Version (K-CPT)
- c. Connors' Rating Scales-Revised
- d. Verbal Fluencies-NEPSY(semantic)
- e. Design fluency-NEPSY

4. Motor function summary score
 - Strength
 - a. Bruininks-Oseretsky Test of Motor Proficiency
 - Fine motor
 - a. Bruininks-Oseretsky Test of Motor Proficiency (BOTMP)-Fine Motor Composite
 - Gross Motor
 - a. Bruininks-Oseretsky Test of Motor Proficiency (BOTMP)-Gross motor composite
 - b. NEPSY-praxis
5. Self-image summary score-Males less than 21 years of age
 - Social Function (Competence)
 - a. Behavior Assessment System for Children (BASC)
 - b. Child Behavior Checklist (CBCL)
 - Affect and Behavior
 - a. Revised Child's Manifest Anxiety Scale (RCMAS)

IV. Clinical trial substudy: Boys with Klinefelter's syndrome will enter the study at ages 4-12 years. At baseline, they will have a history and physical examination, cognitive and behavioral assessment, and further genetic evaluation. All potential subjects will have a full screening to determine eligibility before randomization. They will be randomized (double-blind) to one of two treatment groups: oxandrolone 0.06 mg/kg/day, or placebo control for two years. All subjects will be evaluated for safety at baseline, 3, 6, 12, 18 and 24 months, and after one and two years for end-point efficacy (cognitive and behavioral assessment).

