Post-Study Visit: Per the recommendation of the Data Safety and Monitoring Board (DSMB) all study participants will be invited back for a post-study visit. This visit will occur approximately 6-28 months post-study for patients who have enrolled in the study. The post-study visit will include a history, physical examination, fasting blood work, bone age x-ray, photographs, and cognitive testing. Patients will be reimbursed \$50.00 for completion of the visit. Patients who are unable to travel to a post-study visit or who live farther than driving distance will be asked to have a blood sample drawn locally and sent to our office in Philadelphia.

ANALYSIS

The analysis will be performed in consultation with the statistician, [name] who has been collaborating with [name] for the past 15 years. The analyses described below will include 2 groups of KS boys. All results will be based on gender and age-specific standardized scores. Analysis for safety will be performed at 3, 6, 12, 18, and 24 months and an efficacy analysis for summary scores encompassing all cognitive and behavioral variables will be performed at 12 and 24 months.

I. Safety: An analysis of safety parameters will be performed for the 3, 6, 12, 18 and 24 month values based on a two-way ANCOVA, adjusting for baseline values, comparing the active treatment group versus the placebo. The safety parameters are: systolic and diastolic blood pressure, HDL, LDL cholesterol, liver function (ALT), bone age advancement, or signs of puberty (pubic hair).

II. Primary efficacy (Hypotheses 1 a,b,c): The analysis comparing androgen-treated to placebo-treated KS subjects for the one and two-year measurements will be based on the analysis of covariance (ANCOVA). We will perform a two-way ANCOVA for the five primary outcome measures at 12 and 24 months, comparing the treatment group versus the placebo, adjusting for baseline values and socioeconomic status. There will be a total of 5 summary scores. Each score will be the sum of component z-scores based on gender and age-specific normative values. The summary scores include 1. General cognition, 2. Language, 3. Working memory/executive function and attention, 4. Motor function, and 5. Self-image and behavior. The alpha level for statistical significance will be set at 0.01 for each of the five primary outcome results.

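### The study-wide stopping rule counts two events from either arm with no look by arm first, so two events on placebo would end the trial

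*Combined protocol and SAP*

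**What the plan says.** The rule is in Procedures, part IV, under *Safety results necessitating stopping the study*. If at any time "two or more patients develop severe liver function changes or hypertension, the study will be stopped". The text defines neither "severe" nor the level of hypertension meant, and its grammar leaves open whether the first word governs the second. The threshold's only support is the next sentence: "These changes have not occurred with oxandrolone used in a trial with 73 girls with Turner syndrome followed for up to four years".

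Five other places bear on how the rule would work:

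- The list of triggers for reducing or stopping an individual boy's medication (part IV) already covers milder changes. One entry reads "Systolic blood pressure exceeding 95th %ile for age". Others cover diastolic pressure and SGPT above twice the upper limit of normal.
- Under *Criteria for Subject Withdrawal*: "Safety data will be reviewed on an ongoing (blinded) basis by the PI".
- Analysis, I. Safety, plans an ANCOVA at 3, 6, 12, 18 and 24 months, "comparing the active treatment group versus the placebo. The safety parameters are: systolic and diastolic blood pressure", with liver function (ALT) also listed. It is not linked to the stopping rule.
- The DSMB is named once, under *Post-Study Visit*, as the source of a recommendation to invite participants back. Its remit is not described.
- The exclusion criteria remove boys with "Major liver, kidney or other systemic disease", and part IV adds: "All potential subjects will have a full screening to determine eligibility before randomization".

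**The concern.** A placebo arm lets a trial separate what the drug does from what would have happened anyway, and this rule makes no use of it. Boys on placebo are patients too, so their events count towards the two. The wording is mandatory. It leaves no step at which anyone asks which arm the two boys were in, and the person reviewing safety data as they accrue is blinded.

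At stake is a two-year randomized trial that could be terminated on a count that says nothing about oxandrolone. The loss would be the whole trial; the rule does not bias the efficacy comparison. How much this matters depends on how often the stopping event occurs without any drug effect, and the documents do not give that rate.

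**Working it through.** The plan states no operating characteristic for the rule, so there is no figure of its own to reproduce.

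**Inputs.** From the documents: a trigger of 2 patients; 120 boys in the trial, from 180 recruited with about 30% dropout (Study Population); two years of treatment; 0 events in 73 girls followed for up to four years. Assumed: 1:1 allocation (60 per arm), boys independent, the same two-year event probability p in both arms (no drug effect), and a range of values for p.

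**1. Chance of a false stop.** P(2 or more) = 1 − (1−p)^N − N·p·(1−p)^(N−1). For N = 120 and p = 0.01: 1 − 0.99^120 − 1.2 × 0.99^119 = 1 − 0.299 − 0.363 = 0.338.

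| Assumed two-year rate p | N = 120, both arms | N = 180, both arms | 60 placebo boys alone |
|---|---|---|---|
| 0.1% | 0.7% | 1.4% | 0.2% |
| 0.5% | 12% | 23% | 3.7% |
| 1% | 34% | 54% | 12% |
| 2% | 69% | 88% | 34% |

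N = 180 is an upper limit that would need every recruited boy to be randomized and observed for two years. At N = 120 the chance reaches 50% at a rate of about 1.4%.

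**2. Which arm the two boys are in.** Given exactly two events and no drug effect, both are on placebo with probability (60 × 59)/(120 × 119) = 0.248. Both are on oxandrolone with the same probability, and at least one is on placebo with probability 1 − 0.248 = 0.752. This only restates 1:1 allocation once a trigger has occurred and says nothing about how often one occurs.

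**3. What 0 of 73 says about p.** Follow-up of up to four years means exposure is not known exactly, so two cases are worked.

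- All 73 followed for two years: P(0) = (1−p)^73, which is 48% at p = 1%, 23% at 2% and 2.4% at 5%. The one-sided 95% upper bound is 1 − 0.05^(1/73) = 4.0%.
- All 73 followed for four years at constant risk: each girl contributes two two-year periods, so P(0) = (1−p)^146. This is 23% at 1%, 5% at 2% and 0.06% at 5%. The upper bound is 1 − 0.05^(1/146) = 2.0%.

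The bound on the two-year rate therefore lies between about 2.0% and 4.0%. It would be looser still if some girls were followed for less than two years or were not all observed for these events.

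**The case against.** The strongest reply is that the problem nearly vanishes on the more natural reading of the rule. Raised blood pressure and raised SGPT are already handled boy by boy, so the study-wide rule presumably means something worse. The exclusions, the screening and the absence of events in the Turner trial all point to a low rate. At 0.1% the false-stop risk is under 1%, and the larger figures need rates that no part of the documents supplies. This stands, and it limits the size of the point. The 0.1% is itself an assumption, however, and the rule sets no threshold that would fix it.

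A reader might infer that any reading above the 95th percentile counts as hypertension, so that the trial is almost sure to stop: at a 5% rate, P(2 or more of 120) is 98.4%. The documents do not support this. Such readings lead to a dose change or to stopping that boy's medication, and a rate of 5% fits poorly with 0 of 73.

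A second reply is that an automatic trip-wire is a legitimate choice for a novel treatment in boys aged 4 to 12. Caution is indeed legitimate, but an immediate pause gives the same protection without committing to termination before the arms are known.

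Third, two events cannot prove an excess even when split by arm, since a 2–0 split against oxandrolone has probability 25% by chance. That is correct. The by-arm look mainly prevents a stop caused by placebo events.

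Finally, a DSMB exists, by-arm safety analyses are scheduled, and nothing forbids the board from being consulted. A reader might infer that the board has no safety role. The documents do not show that either, because its remit is not described. What they do show is that the rule does not call on it.

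**Conclusion.** The point holds as a gap in the rule. Followed as written, two events in either arm end the study, including two on placebo, with no comparison by arm and no DSMB review as a condition. That much rests on the text alone.

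The size is conditional. With no drug effect, 120 independent boys and equal rates in both arms, a false stop has probability 0.7% at a two-year rate of 0.1%, 12% at 0.5% and 34% at 1%. If only severe events count, the risk is probably near the bottom of that range. The Turner data do not exclude a rate near 1%. A rate of 2% has only weak support, because it sits at the upper bound if all the girls were followed for four years, so the 69% figure should not be read as a likely outcome. Failing to exclude a rate is not evidence for it, and the girls are a different population. This is a worthwhile, inexpensive improvement and not a fault that undermines the trial.

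**What to change.** Keep the trigger at two patients, and change what it sets off:

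- When the second patient meets the criterion, pause dosing and enrolment at once.
- Have the research pharmacy, which performs the randomization, send the event counts by arm to the existing DSMB. The PI stays blinded.
- Have the DSMB decide promptly whether the study stops or resumes.
- State that the stopping event is more severe than the individual triggers in part IV (blood pressure above the 95th percentile, SGPT above twice the upper limit). The clinical threshold is for the investigators to set.

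The cost is a few lines of protocol text and one by-arm count. There are two downsides. The final stop is no longer automatic, although the pause protects the boys meanwhile. If the trial resumes there is a treatment gap, which matters because the 24-month duration was chosen after a motor effect appeared at 24 but not 12 months in the Turner trial. That gap still costs less than the termination the rule now requires.
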